Obese men and women (BMI 30-40 kg/m²) will be recruited for this study who are between 30-50 years of age and sedentary (<2 hours/week of planned physical activity). Individuals with normal glucose tolerance (NGT), pre-diabetes, and newly diagnosed type 2 diabetes will be enrolled. Normal glucose tolerance is defined as a HbA1c of <5.7%, pre-diabetes as a HbA1c of 5.7-6.4%, and type 2 diabetes as a HbA1c of \geq 6.5% (31). Oral contraceptive use is allowed as long as women don't change their use, or lack thereof, during the course of the study. Exclusion criteria include: regular exercise more than 2 hours/week, medications that could affect glucose, lipid metabolism, thyroid disease, a history of lung disease, pregnancy, active cigarette smoking and severe plasma lipid disorders.

Inclusion criteria:

BMI: 30-40 kg/m²
Age: 30-50 years
Planned physical activity: <2 hrs/week
Glucose tolerance: NGT, pre-diabetes, and Type 2 diabetes
Normal glucose tolerance (NGT) is defined as HbA1c of <5.7%, pre-diabetes as HbA1c of 5.7-6.4%, and type 2 diabetes as HbA1c of ≥6.5% (31).
Oral contraceptive use: Yes or No as long as there is no change during the study
Medications: not taking TZD's, insulin
Thyroid status: TSH between 0.5-5.0 mU/L
Pregnancy status: Not pregnant
Nonsmoker (tobacco and any form of marijuana use)
Fasting TG <400mg/dl
FSH < 20 IU/L

C. Study Design and Research Methods

Ninety-two individuals (30-50 years old) will be screened to recruit sixty-nine obese men and women into the study. Individuals with and without prediabetes will be recruited to achieve a range of starting insulin sensitivities without confounding effects of medications used to treat type 2 diabetes. Volunteers will undergo an insulin clamp before and after block randomization by sex and pre-diabetes strata equally across intervention groups, into a three month

intervention consisting of: 1) endurance exercise training without weight loss, 2) diet-induced weight loss, or 3) delayed intervention control (Figure 5). The three month intervention will result in significant gains in fitness, weight loss, and improvements in insulin sensitivity, but is short enough to maximize retention.

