Exercise training and weight loss will differentially change DAG and sphingolipid content (11), revealing distinct changes in lipid localization, cellular signaling, metabolic function, and improvements in insulin sensitivity. We are expecting a 25% dropout rate, and are powered to complete testing on 17 individuals per group (51 total individuals). Subjects will be tested 48 hours after the last exercise bout to minimize acute exercise effects on insulin sensitivity. Women will be pre-menopausal and tested during the follicular phase (days 1-10) of the menstrual cycle to control for effects on insulin sensitivity.

Preliminary screening- Subjects will arrive after an overnight fast to the outpatient Clinical Translational Research Center (CTRC), and a fasting blood sample will be taken for a standard lipid panel, fasting glucose, TSH, and HbA1c. Women will take a pregnancy test. A physician will perform a history and physical, and subjects will fill out a dietary questionnaire, the NIH Dietary History Questionnaire II (DHQII), and the IPAQ physical activity questionnaire (33).

Strength and Exercise testing, body composition, maximal mitochondrial respiration, and MRI – Eligible subjects will undergo a Kin-Kom isokinetic dynamometer quadriceps strength test, Balke treadmill test to measure maximal work capacity (VO₂max) (34), a DEXA scan to determine body composition, a non-invasive test of maximal mitochondrial respiration, and MRI scan to measure leg muscle and fat mass, and liver fat content. During the maximal mitochondrial respiration test, volunteers will lie down on a table, and we will have a near infrared spectrometer measurement unit strapped to their leg. This unit uses a laser to measure the oxygen levels in the muscle. A blood pressure cuff will be wrapped around their upper thigh. To start the test, we will ask volunteers to make a muscle contraction for 20 seconds, after which we will intermittently inflate and deflate the blood pressure cuff every 5-10 seconds over a 5 minute period. This test will then be repeated. The total time for this test is 30 minutes.

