Aim 1: Our statistical methods are rigorous with an a priori statistical analysis plan to test our hypothesis in an unbiased manner, and power analysis based on our own preliminary data. Prior to analysis, data will be analyzed for normality, and any non-normally distributed variables will be log-transformed for use in analytic models. Correlations between the change in sarcolemmal DAG and sphingolipid species and the change in insulin sensitivity will be performed using Pearson's correlation coefficients in the entire study group (n=51). Then, data comparing changes in sarcolemmal DAG and sphingolipid species to changes in insulin sensitivity before and after the intervention will be analyzed using a one-way Analysis of Variance (ANOVA) to examine overall differences between the intervention groups, and using Tukey's procedure to make pair-wise comparisons (e.g control vs. exercise, control vs. diet only) while adjusting for multiple comparisons. Changes in individual DAG and ceramide species will be examined using the Benjamini Hochberg procedure to limit false discoveries (62), and then Principal Component Analysis (PCA) will be used to examine groups of DAG and ceramide species (13). Analyses will be conducted using SAS statistical software ver. 9.4 (Cary, NC). The power analysis is based on changes in sarcolemmal lipids assuming there will be no significant changes in the control intervention. With an overall n of 51, we will have 92% power to detect a Pearson correlation coefficient similar to our preliminary data (Figure 2B, r= -0.45), and 80% power to detect a correlation coefficient as small as -0.38. Pilot data showed sarcolemmal C18:0 ceramide decreased 0.041 ng/ug protein with a SD of .02 after the combined intervention. With an n of 17/group we will have 84.6% power to measure a similar change in sarcolemmal DAG and sphingolipids for individual group comparisons using the Tukey procedure. The type 1 error rate (alpha) will be set at 5% for all comparisons.

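### Type 2 diabetes is eligible but has no place in the pre-diabetes strata, so this class is not balanced by design and the group comparison does not adjust for it

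*Combined protocol and SAP*

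**What the plan says.** Section IV.B (Description of Population to be Enrolled) states: "Individuals with normal glucose tolerance (NGT), pre-diabetes, and newly diagnosed type 2 diabetes will be enrolled". The inclusion list repeats it: "Glucose tolerance: NGT, pre-diabetes, and Type 2 diabetes". The classes are set by HbA1c and do not overlap: below 5.7% is NGT, 5.7 to 6.4% is pre-diabetes, and 6.5% or above is type 2 diabetes.

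Section IV.C (Study Design and Research Methods) describes the recruits with two classes only: "Individuals with and without prediabetes will be recruited to achieve a range of starting insulin sensitivities". Allocation to the three arms is by "block randomization by sex and pre-diabetes strata equally across intervention groups". No section names a type 2 diabetes stratum, limits how many such participants may enter, or gives a block size.

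Section IV.F (Data Analysis Plan), Aim 1, compares the arms with a "one-way Analysis of Variance (ANOVA) to examine overall differences between the intervention groups", followed by Tukey's procedure. Aim 2 uses the same approach. Neither model contains glycaemic class, sex or a baseline value.

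**The concern.** The glycaemic stratum exists to spread starting insulin sensitivity evenly over the arms. Three classes are enrolled and the stratum has two levels, so one class has no stated home. Read literally, the no-pre-diabetes level pools HbA1c below 5.7% with HbA1c of 6.5% or above, the two ends of the scale that the factor is meant to control. Whoever prepares the allocation list has to guess what was intended.

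At stake is comparability in small arms: 23 randomised and 17 completing. If glycaemic class affects the change in muscle lipids or insulin sensitivity, a chance surplus of participants with type 2 diabetes in one arm adds to or hides part of the apparent intervention effect. The planned ANOVA would not correct for it.

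**Working it through.** **1. Arm size.** Section IV.C plans 17 completers per group with 25% dropout. 17 / (1 − 0.25) = 22.7, rounded up to 23, and 3 × 23 = 69. This reproduces the plan's enrolment: "Ninety-two individuals (30-50 years old) will be screened to recruit sixty-nine obese men and women into the study".

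**2. Where type 2 diabetes falls.**

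| Class | HbA1c (IV.B) | Meets pre-diabetes definition? | Stratum, read literally (IV.C) |
|---|---|---|---|
| NGT | <5.7% | no | without |
| Pre-diabetes | 5.7–6.4% | yes | with |
| Type 2 diabetes | ≥6.5% | no | without |

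**3. Size of chance imbalance, ignoring strata.** Let T be the number with type 2 diabetes among the 69. The documents do not give T, so a range is needed. The chance of the split (a, b, c) with a + b + c = T is

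C(23,a) × C(23,b) × C(23,c) / C(69,T).

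Sum this over splits whose largest and smallest counts differ by 3 or more.

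- T = 2: impossible, 0%.
- T = 3: all three in one arm. 3 × C(23,3) / C(69,3) = 5,313 / 52,394 = 10%.
- T = 4: splits 4-0-0 and 3-1-0. (3 × 8,855 + 6 × 1,771 × 23) / 864,501 = (26,565 + 244,398) / 864,501 = 31%.

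The same sum for larger T:

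| T | 5 | 6 | 8 | 9 | 10 | 12 | 14 | 15 |
|---|---|---|---|---|---|---|---|---|
| Chance of a difference ≥3 | 36% | 35% | 51% | 48% | 58% | 56% | 65% | 61% |

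The values do not rise steadily, because an even split is possible only when T is a multiple of 3. Across T = 8 to 15 the extremes are 48% (T = 9) and 65% (T = 14).

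**4. Effect of the strata.** Stratified block randomisation of 69 participants was simulated, 4,000 runs per setting for T = 6, 12 and 18, with a separate simulation for T = 10. Assumptions, none of them in the documents: sexes equally likely, the remainder split evenly between NGT and pre-diabetes, blocks of 3 or 6. Chance of a difference of 3 or more:

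| T | Pre-diabetes yes/no | Cut at 5.7% | Three levels, blocks of 3 | Three levels, blocks of 6 |
|---|---|---|---|---|
| 6 | 32–33% | about 32% | 0% | 12% |
| 10 | about 55% | about 54% | 0% | about 7% |
| 12 | 51–52% | 51–52% | 0% | 6% |
| 18 | 59% | 58–59% | 0% | 8% |

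The 0% is structural. With three levels, type 2 diabetes occupies two cells (one per sex). With blocks of 3, the arms can differ by at most 1 within a cell, hence by at most 2 in total.

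Both two-level schemes leave type 2 diabetes about as uneven as ignoring strata would.

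**The case against.** - **Randomisation is not compromised.** Type 2 diabetes is balanced in expectation under any of these schemes, and chance imbalance is already reflected in the ANOVA error rate. This stands. A reader might infer that the comparison is biased, but nothing in the documents supports that.
- **The evidence that this class stands apart is indirect.** A reader might infer from section III that lipids and insulin sensitivity differ most between type 2 diabetes and the other groups. The reported contrasts are mainly against lean volunteers, who are not enrolled here (BMI 30–40). For PKC epsilon both the obese and the type 2 diabetes groups exceed lean, and for mitochondrial/ER DAG lean exceeds both. No pre-diabetes group is reported. That type 2 diabetes is the most insulin-resistant class enrolled is a reasonable inference, not a documented finding.
- **The number may be small.** Eligibility is limited to newly diagnosed disease at age 30 to 50, with medications that could affect glucose excluded. With two or three such participants the imbalance hardly matters. This stands, and is why the range starts at 2.
- **The phrase may be shorthand** for all glycaemic classes, or for NGT against everything above it. The documents do not say. The first reading would remove the stratification gap. The second would not balance type 2 diabetes, as the 5.7% column shows.
- **Head-counts are not consequences.** Outcomes are within-person changes, and the documents give no figure for how change depends on class. The effect on estimates, power or error rate therefore cannot be sized. This stands.

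**Conclusion.** The eligibility text and the strata text do not fit together. As written, type 2 diabetes shares a stratum with NGT and is not balanced by design, and the group model does nothing to compensate. This is an ambiguity plus an avoidable exposure to chance imbalance, not a flaw that invalidates the trial.

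Its size depends on an unstated count: negligible at 2 or 3 participants with type 2 diabetes, roughly one chance in three of a difference of three or more at 4 to 6, and about one in two to two in three at 8 to 15. These figures assume 23 per arm at randomisation and describe head-counts only. Because the remedy in the analysis is nearly free, it is worth making even if few such participants enrol.

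**What to change.** 1. **Reconcile the text.** State in IV.C which stratum a participant with HbA1c of 6.5% or above enters, give the block size, and bring the two-class recruitment sentence into line with IV.B.
2. **Adjust the analysis.** In IV.F, Aims 1 and 2, add three-level HbA1c class and sex to the between-group model and make the Tukey comparisons on the adjusted means. Both factors are already available, HbA1c from the screening visit. The cost is 2 + 1 = 3 degrees of freedom, which takes the residual from 51 − 3 = 48 to 45. This also covers participants already randomised.
3. **For future participants, preferably stratify on three levels** (<5.7%, 5.7–6.4%, ≥6.5%) by sex, with small blocks. The downside is six cells for 69 participants, some of them sparse. Blocks of 3 also make the next assignment easier to guess if staff know the block size.

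A two-level cut at 5.7% keeps four cells and stops NGT and type 2 diabetes sharing a stratum. It does not reduce the type 2 diabetes imbalance, so it is adequate only together with step 2.

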The following morning, an antecubital catheter will be placed in one arm for infusions, and another placed in a distal hand vein in the contra-lateral arm for blood draws using the heated hand vein technique (37). After 30 minutes of rest, a baseline blood sample will be taken for metabolic substrates, hormones, and cytokines. Thereafter, a primed (0.03mg/kg), constant infusion (0.04mg/kg/min) of [6,6-²H₂]glucose and [U-¹³C]glucose, as well as a constant infusion (0.03µmol/kg/min) of [U-¹³C]palmitate will begin. The glucose and palmitate stable isotope infusions will continue through the end of the study and will be used to determine hepatic glucose production, peripheral glucose disposal, and muscle *de novo* DAG and sphingolipid synthesis. After 2 hours of infusion, a percutaneous needle biopsy will be taken midway

between the greater trochanter of the femur and patella. Then a standard 3 hour hyperinsulinemic/euglycemic clamp will follow as described by DeFronzo with insulin infused at 40 mU/m²/min, and glucose clamped at 90mg/dl with a variable dextrose infusion (38). Dextrose infused to maintain euglycemia will be "spiked" with [6,6-²H₂]glucose to minimize changes in isotopic enrichment. Blood will be sampled every 5 minutes to determine glucose concentration and the dextrose infusion adjusted as necessary. A second muscle biopsy will be taken from the contra-lateral limb 1 hour into the insulin clamp to measure insulin-stimulated insulin signaling. Blood samples will be taken over the final 30 minutes for substrate, hormone, and cytokine analyses. Isotopically measured glucose rate of disappearance will be measured during the last 30 minutes of the 3 hour clamp, normalized to plasma insulin concentration, and used as a measure of whole body insulin sensitivity (39).

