Muscle biopsy – Subcellular fractionation will be performed as described in Figure 1. Diacylglycerol (1,2- and 1,3- isomers), sphingolipids (dihydroceramide, ceramide, glucosylceramide, lactosylceramide, sphingosine, sphingosine-1-phosphate, sphingomyelin), triacylglycerol, phosphatidic acid, and long chain acyl-CoA species will be analyzed by [name] using the lipidomics platform in our laboratory. Subcellular fractions are fortified with internal standards (ISs), lipid extracted, and analyzed by an Agilent 1100 HPLC connected to an API 2000 triple quadrupole mass spectrometer (40). The 1,3- and 1,2- DAG isomers are separated chromatographically using a Hilic 2.1 micron, 3x100mm column. Concentration is determined by comparing ratios of unknowns to odd chain or deuterated internal standards. Incorporation of [U-¹³C]glucose into DAG glycerol, and [U-¹³C] palmitate into the sphingolipid backbone will be used to estimate *de novo* synthesis of DAG and sphingolipids (41; 42). Western blot analysis will quantify PKC translocation of θ , ε , β II, and δ isoforms in basal biopsies, as well as insulin signaling in basal and insulin stimulated biopsies including AKT^{ser473} /total, IRS-1^{Tyr612}/total, and AS160^{Thr642}/total using standard techniques (43). AKT^{Thr34} phosphorylation will be used to estimate PKC ζ activation by ceramide. PP2A activity will be measured using manufacturer instructions (Ser/Thr Phosphatase Assay Kit 1, Billerica, MA).

After the baseline clamp, subjects will be randomized into one of three interventions for three months:

1. Endurance exercise training - Participants will undergo supervised endurance exercise training administered by the Nutrition Obesity Research Center (NORC) Energy Balance Core (see attached letter of support from [name]) using well-established methods (44-48). Participants will perform supervised exercise 4x/week as well as exercise 1x/week on their own. Each 60 min session will include a short warm-up, 40 to 50 min of endurance exercise, and a cool-down. The exercise program will consist primarily of brisk walking or jogging, and will be supplemented with rowing, stepping, or elliptical exercise. The initial exercise prescription will be 30 minutes at 65% of maximal HR. During the first 2 weeks of training, exercise duration and intensity will be gradually increased

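### The glucose-tracer prime as written (0.03 mg/kg) equals 45 seconds of the written infusion (0.04 mg/kg/min), so the infusion is in effect unprimed; if dosed that way, the level of DAG-glycerol synthesis could be understated.

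*Combined protocol and SAP*

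**What the plan says.** The Insulin clamp study paragraph (section IV.C) describes a "primed (0.03mg/kg), constant infusion (0.04mg/kg/min) of" [6,6-²H₂]glucose and [U-¹³C]glucose, alongside a palmitate tracer infused at its own rate. No other glucose prime appears anywhere in the document.

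The timing is: "After 2 hours of infusion, a percutaneous needle biopsy will be taken midway" on the thigh, then a 3-hour clamp. The infusions run to the end and "will be used to determine hepatic glucose production, peripheral glucose disposal", together with muscle de novo synthesis of DAG and sphingolipids. For insulin sensitivity, the "glucose rate of disappearance will be measured during the last 30 minutes of the 3 hour clamp", with labelled glucose added to the dextrose.

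The Muscle biopsy paragraph takes incorporation of labelled "glucose into DAG glycerol, and" of labelled "palmitate into the sphingolipid backbone will be used to estimate" de novo synthesis. It does not say which biopsy supplies the DAG labelling or which precursor enrichment is the divisor. No method is stated for basal glucose production.

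On blood sampling, the text has "a baseline blood sample will be taken for metabolic substrates, hormones, and cytokines. Thereafter, a primed" infusion begins, 5-minute glucose checks during the clamp, and "Blood samples will be taken over the final 30 minutes for substrate, hormone, and cytokine analyses".

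**The concern.** A prime is meant to fill the body's glucose pool with tracer at the start, so that enrichment is near plateau when measurements are made. A prime worth 45 seconds of infusion cannot do that. The two dose figures do not fit together as a primed infusion.

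If the dose was given as written, muscle would be exposed to a rising precursor enrichment throughout the 2 hours before the basal biopsy. Dividing the label found in DAG glycerol by the plateau or 2-hour enrichment would then understate synthesis. A steady-state calculation of basal glucose production near 2 hours would be too high.

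De novo synthesis before and after the interventions is among the measurements proposed in section I. Section II counts on it to explain how lipid accumulates in membranes. That question depends on the level of synthesis as well as its change.

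**Working it through.** **Step 1: the ratio (no assumptions).** Inputs from section IV.C, Insulin clamp study: prime 0.03 mg/kg, infusion 0.04 mg/kg/min, first biopsy at 120 min.

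- Prime in minutes of infusion: p = 0.03 / 0.04 = 0.75 min = 45 s.
- Share of tracer given by 2 hours: 0.03 / (0.03 + 0.04 × 120) = 0.03 / 4.83 = 0.6%.

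It is unclear whether the dose applies to each glucose tracer or to both together; the ratio is the same either way.

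**Step 2: what that would do (assumptions, none from the documents).** One glucose pool; fractional turnover k of 0.5%, 1%, 2% or 3% per minute; DAG precursor enrichment tracking plasma; labelling read at the 2-hour biopsy.

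- Enrichment as a share of plateau: f(t) = 1 − (1 − p·k)·exp(−k·t).
- Mean share over 0 to 120 min: m = 1 − (1 − p·k)·(1 − exp(−120k)) / (120k).
- DAG synthesis error with a 2-hour divisor: m / f(120) − 1. With a plateau divisor: m − 1. With time-averaged precursor enrichment: 0.
- Error in steady-state basal glucose production at 2 hours: 1 / f(120) − 1.

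Example, k = 0.01: f(120) = 1 − 0.9925 × 0.3012 = 0.701; m = 1 − 0.9925 × 0.5823 = 0.422; 0.422 / 0.701 = 0.602, so synthesis is understated by 40%; 1 / 0.701 − 1 = 43%.

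| k per min | f(120) | f(120), no prime | m | DAG error, 2-hour divisor | DAG error, plateau divisor | Glucose production error |
|---|---|---|---|---|---|---|
| 0.005 | 0.453 | 0.451 | 0.251 | −45% | −75% | +121% |
| 0.01 | 0.701 | 0.699 | 0.422 | −40% | −58% | +43% |
| 0.02 | 0.911 | 0.909 | 0.627 | −31% | −37% | +10% |
| 0.03 | 0.973 | 0.973 | 0.736 | −24% | −26% | +3% |

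The written prime adds only 0.06 to 0.23 percentage points to 2-hour enrichment. A prime that reaches plateau at once is 0.04 / k, which is 8, 4, 2 or 1.3 mg/kg.

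**Step 3: before/after change.** Assume turnover rises 25% with the pool constant. For k from 0.01 to 0.0125, f(120) goes from 0.701 to 0.779 and m from 0.422 to 0.487.

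- DAG ratio after/before, 2-hour divisor: (0.487 / 0.779) / (0.422 / 0.701) = 1.04, a spurious shift of 4%. Across the four values of k: 2% to 5%.
- DAG ratio, plateau divisor: 0.487 / 0.422 = 1.15, a shift of 15%. Across k: 7% to 20%.
- Steady-state basal glucose production: a true +25% reads as 1.25 × 0.701 / 0.779 − 1 = +12.5%. Across k: about +7% to +23%.

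**Step 4: the clamp measurement.** The last 30 minutes of a 3-hour clamp fall 270 to 300 min after tracer start, ignoring the time taken by the biopsy. Under basal kinetics f(270) is 0.74, 0.93, 1.00 and 1.00. The labelled dextrose, and the faster turnover expected under insulin, should bring the slow cases closer to plateau; this was not modelled.

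**The case against.** **It is probably a slip.** A prime of 3 mg/kg would be 3 / 0.04 = 75 minutes of infusion, inside the range in step 2. If something like that was given, none of the modelled errors occurred. This stands, and it is why the first action is to check the records. It does not remove the point: this is an operative dose in the governing protocol, nothing else in the document corrects it, and it is wrong as written.

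**The sizes come from assumptions.** Also true. The documents give no turnover, pool, divisor or biopsy assignment. They refer the synthesis method to cited papers that could not be consulted. An error range of 3% to 121% for glucose production says only that the error could be trivial or large.

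**The sampling list.** A reader might infer that, with no sample listed between tracer start and the basal biopsy, the plan could neither detect nor correct the rise. The text does not support that. Its list names no enrichment sample at any time, yet isotopic glucose disappearance cannot be obtained without one. The list is therefore not complete, and silence about 0 to 2 hours does not show that nothing is drawn.

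**Bias cancels before and after.** This holds approximately for DAG synthesis with a 2-hour divisor. It does not hold with a plateau divisor, or for steady-state basal glucose production (step 3).

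**Low stakes.** Largely right. Synthesis is not among the primary outcomes in section IV.A, which treats other intracellular responses as exploratory, and the analysis and power plans in section IV.F do not mention it.

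**Conclusion.** The point holds, as a minor one. Without any assumption, the written prime is 45 seconds of the written infusion and the infusion is in effect unprimed. The likely explanation is a unit or decimal error in the text.

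The consequences arise only if that dose was given, and their size rests on the one-pool model, the assumed turnover and an unstated divisor. On those terms the level of DAG-glycerol synthesis could be understated by 24% to 45% with a 2-hour divisor and by 26% to 75% with a plateau divisor; time-averaged precursor enrichment removes the error. Basal glucose production could be overstated, and changes in it blunted. All these figures are illustrations.

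It would be tempting to read this as a threat to the trial's main results. The documents do not support that. Sphingolipid synthesis uses the palmitate tracer. Insulin sensitivity is read about 4.5 to 5 hours after tracer start with labelled dextrose, so it is probably little affected, although this was not shown for the slowest turnover. The remaining primary outcomes do not use the glucose tracer.

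**What to change.** Check the prime against the infusion records and correct the figure or unit in the Insulin clamp study paragraph. State there which precursor enrichment divides DAG-glycerol incorporation. If the dose given was adequate, nothing more is needed, and the cost is a text correction.

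If 0.03 mg/kg was really given:

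- **Remaining studies.** Set the prime to the infusion rate divided by the investigators' own expected basal turnover. It should not be rounded up freely: in the same model with a 2-hour divisor, twice the matching prime overstates DAG-glycerol synthesis by 13% to 26%, and half of it understates by 12% to 17%.
- **Studies already run.** Use any plasma samples from 0 to 2 hours to divide DAG-glycerol incorporation by time-averaged precursor enrichment, and use non-steady-state equations for basal glucose production. Where no such samples exist, treat those levels as not interpretable.

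The cost in that case is one dose change, plus enrichment assays on samples already held. Studies run at the written dose without timed samples cannot be fully recovered.
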